10.0 EVALUATION DURING TREATMENT/INTERVENTION

Study	Pre-Treatment	Induction											Follow-up		
		Cycle 1 ⁱ								Cycles 2-8			End of Therapy	1 month after EOT ^{i,j}	1, 2, and 3 years after EOT ^{i,m}
		Day 1	Day 2	Day 8	Day 9	Day 15	Day 16	Day 22	Day 23	Day 1 ^{io}	After completing 4-8 cycles	CR/sCR reached			
Medical Record Review	x												x	x	x
H&P with blood pressure	x	x		x		x				x			x	x	x ^m
Echo + EKG	x										x ⁿ				
ECOG	x									x			x		
Informed Consent	x														
Viral Studies ^b	x									x ^b			x ^b	x ^b	x ^b
Register for RevAssist	x														
Routine Labs ^a	x	x	x	x		x		x		x	x ^a		x		x ^m
Lymphocyte subsets	x									x ^a (only C4D1)			x		
Myeloma tests ^{f,j}	x ^{f,j}									x ^{f,j}			x ^{f,j}		x ^m
Urine for UPEP and IFE ^j	x ^j									x ^j			x ^j		x ^m
Pregnancy Test ^c	x ^{c,d}	x ^d	x ^d	x ^e		x ^e		x ^e		x ^c				x ^e	
Research Blood/Urine	x		x	x		x		x		x		x	x		x ^m
Bone Marrow/Aspirate	x ^g											x ^h	x ^h		x ^m

FDG PET-CT ^k	x												x		
Daratumumab Type and Screen Immunotherapy	x														
Stool Sample collection	X ^o									X ^o			X ^o		
Adverse Events/Toxicity		x								x			x	x	
Daratumumab ^p		x		x		x		x		X ^p					
Carfilzomib ^p		x	x	x	x	x	x			X ^p					
Lenalidomide ^p			x	x	x	x	x	x	x	X ^p					
Dexamethasone ^p		x	x	x	x	x	x	x		X ^p					
Acetaminophen/ ^p Diphenhydramine															
Montelukast ^p		x		x		x		x							

- a. Routine tests include CBC, reticulocyte count, Chem 14, magnesium, phosphate, uric acid, eGFR determination and LDH. Reticulocyte count will only be performed at baseline. PT and PTT will only be performed at baseline. Peripheral blood lymphocyte subsets at baseline, C4D1, and end of therapy. Complete Blood Count (CBC) WITH Differential will be performed on days 8 and 15 during cycles 2-8.
- b. Viral studies include hepatitis B surface antigen (HBsAg), hepatitis B surface antibody (Anti-HBs), and hepatitis B core antibody (Anti-HBc) and Hep C antibody. If Hep C antibody positive, Hep C RNA PCR will be performed.
 - *HPV DNA testing (if applicable)*: For subjects with serologic evidence of resolved HBV infection (i.e., positive Anti-HBs or positive Anti-HBc) at Screening, HBV DNA testing by PCR must be performed locally. Treatment Phase: Q12W during treatment, at the End of Treatment Visit, and Q12W for up to 6 months after the last dose of study treatment. Refer to Section 8.0.

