- m. After 1, 2 and 3-year from completing therapy (+/- 1 month window), PFS and OS data will be collected on all patients. Patients will have formal evaluation with H&P, clinical labs, myeloma labs and bone marrow evaluating for MRD status as per standard of care. PFS and OS data may be collected over the phone along with review of medical records. Survival, PFS, and time to next line of treatment data may be collected on subsequent protocols that patients have consented for (maintenance protocols/bio-banking or storage protocols).
- n. Patients will have an echocardiogram (2-D or strain) performed at baseline and after completion of 6 cycles of therapy. Outside echocardiograms are permissible
- o. Stool samples will be collected prior to start of treatment during screening or before starting cycle 1, after cycle 1 (+14 day permitted) and End of Study (EOS) +/-14 days A food frequency questionnaire will be administered to patients once either on study or in follow up.
- p. The treatment schedule for cycles 1-8 is as follows:

Cohort 1:

- Cycle 1 ONLY: Daratumumab 16 mg/kg days 1, 8, 15, and 22; Carfilzomib 20 mg/m² per dose, days 2 and 3; Carfilzomib 36 mg/m² per dose, days 8, 9, 15, and 16; Dexamethasone 20 mg/dose, days 1, 2, 8, 9, 15, 16 and 22; Lenalidomide 25 mg/day, days 2 – 21 every 28 days; Montelukast 10 mg (first 4 doses of Daratumumab)
- Cycle 2: Daratumumab 16 mg/kg days 1, 8, 15, and 22
- Cycles 3-6: Daratumumab 16 mg/kg days 1 and 15

- Cycles 7-8: Daratumumab 16 mg/kg day 1
- Cycles 2-8: Carfilzomib 36 mg/m² per dose, days 1, 2, 8, 9, 15, and 16
- Cycles 2-8: Lenalidomide 25 mg/day, days 1-21 every 28 days
- Cycles 2: Dexamethasone 20 mg/dose, days 1, 2, 8, 9, 15, 16 and 22
- Cycles 3-4: Dexamethasone 20 mg/dose, days 1, 2, 8, 9, 15 and 16
- Cycles 5- 8: Dexamethasone 10 mg/dose, days 1, 2, 8, 9, 15 and 16

Cohort 2:

- Cycle 1 ONLY: Daratumumab 16 mg/kg days 1, 8, 15, and 22; Carfilzomib 20 mg/m² per dose, day 2; Carfilzomib 56 mg/m² per dose, days 8 and 15; Dexamethasone 20 mg/dose, days 1,2, and 22, 40 mg/dose days 8 and 15; Lenalidomide 25 mg/day, days 2–21 every 28 days; Acetaminophen 650 mg; intravenous Diphenhydramine 25 mg. Montelukast 10 mg will be administered prior to the first 4 doses of Daratumumab.
- Cycle 2: Daratumumab 16 mg/kg days 1, 8, 15, and 22; Acetaminophen 650 mg; intravenous Diphenhydramine 25 mg.
- Cycles 3-6: Daratumumab 16 mg/kg days 1 and 15; Acetaminophen 650 mg; intravenous Diphenhydramine 25 mg.

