11.2 Lenalidomide

Likely Side Effects: those occurring in more than 20% or more than 20 out of 100 persons who receive lenalidomide:

- Low number of white blood cells (with or without fever)
- Anemia (lowered red blood cells)
- Decrease in cells that help your blood clot (lowered platelets)
- Swelling in legs and/or extremities
- Diarrhea
- Constipation
- Nausea
- Feeling weak and unwell, fatigue
- Fever
- Chills
- Rash
- Pain including muscles, joints, back, and non-cardiac chest pain
- Dizziness
- Shaking or tremor
- Shortness of breath
- Upper respiratory tract infection

Less Likely Side Effects: those occurring in 5-20% or 5 to 20 out of 100 persons who receive lenalidomide:

- Vision Blurred
- Altered sense of taste
- Pain or decreased sensation of touch
- Pneumonia
- Urinary tract infection
- Increased sweating
- Dry skin
- Itching
- Decreased appetite
- Weight loss

- Vomiting
- Abdominal pain
- Dry mouth
- Electrolyte imbalance in blood
- Blood clot in lower or upper extremities
- Lowered level of consciousness with drowsiness, listlessness, and apathy
- Abnormal liver lab tests
- Loss of fluid
- Muscle weakness
- Tingling of skin
- High or low blood pressure

Rare and/or Potentially Serious Side Effects: these have occurred in less than 5% or in less than 5 out of 100 persons who receive lenalidomide:

- Lowered white blood cells with fever
- Blood clot to lung
- Irregular heart beat
- Congestive heart failure – abnormal functioning of heart leading to fluid in lungs and extremities
- Stroke
- Immune destruction of red blood cells (autoimmune hemolytic anemia)
- Slow heart rate or fast heart rate
- Heart attack
- Blindness
- Mood swings, hallucinations
- Gastrointestinal bleed
- Severe skin allergic reactions: lining of the nose, mouth, stomach and intestines or rash leading to the separation of the top layer of skin, swelling under the skin
- Rapid death of cancer cells where the accumulating contents of dying cancer cells cause an imbalance in the chemistry of the body which can lead to kidney damage.
- Lenalidomide, a thalidomide analogue, caused limb abnormalities in a developmental monkey study similar to birth defects caused by thalidomide in humans. If lenalidomide is used during pregnancy, it may cause birth defects or death to a developing baby.
- Second primary cancers

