17.2 Serious Adverse Event (SAE) Reporting

An adverse event is considered serious if it results in ANY of the following outcomes:

- Death
- A life-threatening adverse event
- An adverse event that results in inpatient hospitalization or prolongation of existing hospitalization
- A persistent or significant incapacity or substantial disruption of the ability to conduct normal life functions
- A congenital anomaly/birth defect
- Important Medical Events (IME) that may not result in death, be life threatening, or require hospitalization may be considered serious when, based upon medical judgment, they may jeopardize the patient or participant and may require medical or surgical intervention to prevent one of the outcomes listed in this definition

Note: Hospital admission for a planned procedure/disease is not considered an SAE.

SAE reporting is required as soon as the participant starts investigational treatment/intervention. SAE reporting is required for 30-days after the participant's last investigational treatment/intervention. Any event that occurs after the 30-day period that is unexpected and at least possibly related to protocol treatment must be reported.

Please note: Any SAE that occurs prior to the start of investigational treatment/intervention and is related to a screening test or procedure (i.e., a screening biopsy) must be reported.

All SAEs must be submitted in PIMS. If an SAE requires submission to the HRPP office per IRB SOP RR-408 'Reporting of Serious Adverse Events', the SAE report must be submitted within 5 calendar days of the event. All other SAEs must be submitted within 30 calendar days of the event.

The report should contain the following information:

- The date the adverse event occurred
- The adverse event
- The grade of the event
- Relationship of the adverse event to the treatment(s)
- If the adverse event was expected
- Detailed text that includes the following
 - An explanation of how the adverse event was handled

- A description of the participant's condition
 - Indication if the participant remains on the study
- If an amendment will need to be made to the protocol and/or consent form
- If the SAE is an Unanticipated Problem

For IND/IDE protocols:

The SAE report should be completed as per above instructions. If appropriate, the report will be forwarded to appropriate authorities, such as the FDA by the SAE staff through the IND Office

17.2.1

AE/SAE Reporting by Investigator-sponsor to Janssen

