As the sponsor of the Study, PRINCIPAL INVESTIGATOR shall be solely responsible for complying, within the required timelines, any safety reporting obligation to competent Health Authorities, IRB/ECs and any participating (co or sub) investigators, as defined in applicable laws and regulations. For the purposes of this section, safety data includes adverse events, product quality complaints (PQCs), and special situations including pregnancies.

The PRINCIPAL INVESTIGATOR will provide safety information to Janssen Scientific Affairs, LLC on adverse events, special situations including pregnancies and product quality complaints as defined within this section.

This Study has been designated as an interventional study. As such, all adverse events for daratumumab regardless of causality and special situations excluding those from subjects not exposed to a Janssen Medicinal Product and product quality complaints with or without an adverse event as described in this Exhibit will be reported from the time a subject has signed and dated an Informed Consent Form (ICF) until completion of the subject's last study-related procedure (which may include contact for follow-up safety). Serious adverse events will be reported for 30 days after the last dose of study drug.

Reporting to Amgen

Serious Unexpected Suspected Adverse Reactions (SUSARs) will be reported to Amgen.

Pregnancy/Lactation exposures should be reported to Amgen within **10 calendar days** of Sponsor awareness.

Amgen Global Safety reporting information for SUSARs and Pregnancy/Lactation exposures:

- Electronically via Amgen SECURE Email service (preferred) : [contact]
- Facsimile (fax) to: [name]

Adverse Event (AE) Definition:

An adverse event is any untoward medical occurrence in a clinical study subject administered a medicinal (investigational or non-investigational) product. An adverse event does not necessarily have a causal relationship with the treatment. An adverse event can

therefore be any unfavorable and unintended sign (including an abnormal finding), symptom, or disease temporally associated with the use of a medicinal (investigational or non-investigational) product, whether or not related to that medicinal (investigational or non-investigational) product. (Definition per International Conference on Harmonisation [ICH])

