This includes any occurrence that is new in onset or aggravated in severity or frequency from the baseline condition, or abnormal results of diagnostic procedures, including laboratory test abnormalities.

Adverse Event of Special Interest Definition:

Adverse events of special interest are events that Janssen Scientific Affairs, LLC is actively monitoring as a result of a previously identified signal (even if non-serious). These adverse events are:

- Infusion reactions \geq Grade 3
- Infections \geq Grade 4
- Cytopenias \geq Grade 4
- Tumor lysis syndrome
- Other malignancies
- Intravascular hemolysis – all grades

Any Adverse Event of Special Interest that is to be reported to the COMPANY should be recorded on a Serious Adverse Event Report Form and be reported to the COMPANY **within 24 hours of knowledge of the event.**

Individual Case Safety Report (ICSR) Definition:

A valid ICSR must contain the four minimum criteria required to meet regulatory reporting requirements.

- an identifiable subject (but not disclosing personal information such as the subject's name, initials or address)
- an identifiable reporter (investigational site)
- a Janssen medicinal product
- an adverse event, outcome, or certain special situations

The minimum information required is:

- suspected Janssen medicinal product (doses, indication)
- date of therapy (start and end date, if available)
- batch or lot number, if available
- subject details (subject ID and country)
- gender
- age at AE onset
- reporter ID
- adverse event detail (AE verbatim in English), onset date, relatedness, causality, action taken, outcome, (if available)
- Janssen protocol ID

Product Quality Complaint (PQC)

A product quality complaint is defined as any suspicion of a product defect related to a potential quality issue during manufacturing, packaging, release testing, stability monitoring, dose preparation, storage or distribution of the product, or delivery system. Not all PQC's involve a subject. Lot and batch numbers are of high significance and need to be collected whenever available.

Examples of PQC include but not limited to:

- Functional Problem: e.g., altered delivery rate in a controlled release product
- Physical Defect: e.g. abnormal odor, broken or crushed tablets/capsules
- Potential Dosing Device Malfunction: e.g., autoinjector button not working, needle detaching from syringe
- Suspected Contamination
- Suspected Counterfeit

Serious Adverse Event (SAE)

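### The safety-collection windows conflict, and the year 1 to 3 schedule has no item asking about second cancers, a listed risk and an adverse event of special interest

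*Combined protocol and SAP*

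**What the plan says.** **The event.** Section 11.2 places "Second primary cancers" in its rarest category, described as "these have occurred in less than 5% or in less than 5 out of 100 persons who receive lenalidomide". The AESI list in Section 17.2.1 includes "Other malignancies". AESIs go on the SAE form and must reach the daratumumab supplier within 24 hours of the site learning of them.

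**The windows.**
- Section 10.0, grid: the row "Adverse Events/Toxicity" has its last marks at end of therapy and 1 month later. It is blank in the column for years 1, 2 and 3. Section 9.4.4 places a toxicity visit at 1 month.
- Section 9.4.3: visits that assess toxicity continue at 1 month, 1 year and 3 years after therapy.
- Section 17.2: SAE reporting ends 30 days after the last treatment. Beyond that, "Any event that occurs after the 30-day period that is unexpected and at least possibly related to protocol treatment must be reported".
- Section 17.2.1: all daratumumab adverse events, whatever their cause, are reported "until completion of the subject's last study-related procedure". The next sentence reads "Serious adverse events will be reported for 30 days after the last dose of study drug".
- Section 17.2.1, on AESIs: no end date is given.

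**Years 1 to 3.** Footnote m to the grid names PFS, OS, history and physical, laboratory tests and marrow for MRD. It adds "Survival, PFS, and time to next line of treatment data may be collected on subsequent protocols". It does not name new malignancies.

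**Analysis.** Under secondary objective 1, Section 14.0 summarizes toxicities by grade and by treatment cycle.

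**The concern.** The plan treats second cancers as important enough for 24-hour reporting, but no follow-up contact is told to ask about them. A duty that starts when the site learns of an event does not make the site look for it. If staff work from the grid, footnote m and the 30-day SAE rule, they would not record these events systematically. Because AESIs use the SAE form, staff may also apply the SAE time limit to them.

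The two adjacent sentences in Section 17.2.1 compound this: read literally, serious events have a shorter window than non-serious ones.

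Safety is secondary objective 1. A second cancer found after therapy belongs to no cycle, so even a recorded case has no stated place in the summary. A low or zero count could not be read as evidence of low risk, because it might only reflect which section the site followed.

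**Working it through.** The plan states no figure to reproduce. The check compares the clauses, then sizes the gap.

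**1. Clauses side by side for a second cancer found 2 years after therapy**

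| Source | Is it recorded or reported? |
|---|---|
| 10.0 grid, AE row | No assessment scheduled after 1 month |
| 9.4.3 | Toxicity visits at 1 and 3 years; malignancy not named |
| 10.0 footnote m | Examination and record review, but no malignancy item |
| 17.2, 30-day SAE limit | Outside the window |
| 17.2, later clause | Only if judged unexpected and at least possibly related |
| 17.2.1, all daratumumab AEs | Yes, if the year-3 evaluation counts as the last study-related procedure |
| 17.2.1, SAEs | Outside the 30-day window |
| 17.2.1, AESIs | Yes, once the site knows of it |

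The same event is reportable under some clauses and outside others. None of them prompts the question.

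**2. Share of planned time after the grid's last AE mark**

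Inputs: 8 cycles of 28 days (Section 9.0) and 3 years of follow-up (Section 9.5.2). The 1-month visit is taken as 30 days.
- Therapy: 8 × 28 = 224 days.
- Follow-up: 3 × 365 = 1,095 days.
- Total: 224 + 1,095 = 1,319 days.
- To the last AE mark: 224 + 30 = 254 days, and 254 / 1,319 = 19%.
- After it: 1,319 − 254 = 1,065 days, and 1,065 / 1,319 = 81%.

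With one 7-week harvest delay (49 days), the total is 1,368 days and the share is 1,065 / 1,368 = 78%.

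**3. How many cases could be involved**

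The documents give only an upper category of 5%, with no point estimate and no timing. The incidences below are assumptions over a patient's whole time on study. Expected cases = 82 × p. The chance of at least one case = 1 − (1 − p)^82.

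| Assumed p | Expected cases in 82 | Chance of at least one |
|---|---|---|
| 1% | 0.8 | 56.1% |
| 2% | 1.6 | 80.9% |
| 3% | 2.5 | 91.8% |
| 5% | 4.1 | 98.5% |

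Per cohort of 41, the expected number runs from 0.4 to 2.1 (41 × 0.01 to 41 × 0.05). With counts this small, one or two missed cases would change the result.

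**4. Hepatitis B**

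Footnote b continues HBV DNA testing in applicable patients for up to 6 months after the last dose. The grid's last AE mark is at 1 month. Section 17.2.1 counts abnormal test results as adverse events, so the all-AE window could cover a late reactivation. The grid and the 30-day rule do not show this.

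**The case against.** A reader might infer that adverse-event collection stops 1 month after therapy, that late second cancers are not captured, and that the AESI duty could not be met. The documents do not support this. Section 17.2.1 carries all daratumumab adverse events to the last study-related procedure and puts no end date on AESIs. Section 9.4.3 assesses toxicity at 1 and 3 years. The grid marks record review and a history and physical in years 1 to 3, where a new cancer could come to light. The grid's AE row is also not a strict collection window: in cycle 1 it is marked only on Day 1, although Section 9.4.3 assesses toxicity on Days 8 and 15 too.

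A reader might also infer that second cancers fall outside the later clause of Section 17.2 because Section 11.2 lists them and so makes them expected. That does not follow. For daratumumab, Section 17.2.1 judges expectedness by the Investigator's Brochure, which is not among the documents. Second cancers appear in the lenalidomide list and not in the daratumumab list. The clause neither clearly includes nor clearly excludes them.

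Other points on this side are fair. The documents say nothing about when second cancers arise. Patients may go on to maintenance or transplant, so attribution to eight cycles of this regimen would be weak. The primary endpoint, the two-stage design and the suspension rule do not depend on this point.

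These arguments remove the absolute readings. They do not reconcile the windows or supply a question at years 1 to 3, and attribution can be handled by recording later therapy.

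**Conclusion.** The point holds as a conflict between windows plus a missing follow-up item. At least four end points coexist (about 1 month, 1 and 3 years, the last study-related procedure, and none), and Section 17.2.1 gives serious events less time than other adverse events. An AESI that is also a listed risk may be recorded in years 1 to 3 only if it happens to come to notice.

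The 81% (78% with a harvest delay) assumes all 8 cycles and the full 3 years of follow-up. It measures time without an assessment scheduled in the grid's AE row. The case counts of 0.8 to 4.1 rest on an assumed incidence of 1% to 5%. They indicate scale and do not predict how many cases would be missed, since timing is unknown and some cases would be noticed anyway.

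This affects the safety objective and safety reporting. It is worth correcting because the remedy is specific and small.

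**What to change.** 1. In the Section 10.0 grid and footnote m, add one item at the existing 1-, 2- and 3-year contacts: new malignancy (yes/no, type, date). It can be collected by telephone or record review, as PFS and OS already are.
2. In Sections 17.2 and 17.2.1, state that new malignancies are reported as AESIs to the end of the 3-year follow-up, regardless of the 30-day SAE limit or expectedness.
3. Reconcile the AE and SAE windows across Sections 9.4.3, 9.4.4, 10.0, 17.2 and 17.2.1. Say which visit is the last study-related procedure, and how the windows fit the 6-month HBV DNA testing in footnote b.
4. In Section 14.0, add a summary of second cancers by cohort with follow-up time, noting any subsequent therapy.

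The cost is protocol wording and one extra field, with no new visit or procedure. The late-toxicity report may look slightly less favourable, and attribution will stay limited by later maintenance or transplant.

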18.0 INFORMED CONSENT PROCEDURES

Before protocol-specified procedures are carried out, consenting professionals will explain full details of the protocol and study procedures as well as the risks involved to participants prior to their inclusion in the study. Participants will also be informed that they are free to withdraw from the study at any time. All participants must sign an IRB/PB-approved consent form indicating their consent to participate. This consent form meets the requirements of the Code of Federal Regulations and the Institutional Review Board/Privacy Board of this Center. The consent form will include the following:

1. The nature and objectives, potential risks and benefits of the intended study.
2. The length of study and the likely follow-up required.
3. Alternatives to the proposed study. (This will include available standard and investigational therapies. In addition, patients will be offered an option of supportive care for therapeutic studies.)
4. The name of the investigator(s) responsible for the protocol.

5. The right of the participant to accept or refuse study interventions/interactions and to withdraw from participation at any time.

Before any protocol-specific procedures can be carried out, the consenting professional will fully explain the aspects of patient privacy concerning research specific information. In addition to signing the IRB Informed Consent, all patients must agree to the Research Authorization component of the informed consent form.

Each participant and consenting professional will sign the consent form. The participant must receive a copy of the signed informed consent form.

